3.0 Mechanism of Action of N115

Sodium pyruvate is a natural antioxidant, and as an antioxidant has been shown to significantly reduce inflammatory agents throughout the human body including the lungs and nasal passages. The reduction of inflammatory agents including IL-6 the cause of the cytokine storm in COVID-19 patients. Nasal congestion does not allow nitric oxide to be produced by nasal cells and released into the nasal cavities. A previous study with Pulmonary Fibrosis patients clearly demonstrated a significant increase in exhaled nitric oxide, and since nitric oxide has been shown to kill virus, including COVID-19, this trial is being designed to determine if the N115 Sodium pyruvate-based nasal spray will i increase in nasal nitric oxide to the extent that COVID-19 viral loads are reduced or eliminated.

In over six human clinical trials submitted to the FDA, with pulmonary fibrosis, COPD and Cystic fibrosis patients, N115 reduced lung inflammation by reducing inflammatory cytokines including the IL-6 cytokine that causes the so-called cytokine storm in COVID-19 patients and did this with no known adverse reactions.

In a Phase III Placebo Controlled Clinical Trial with Idiopathic Pulmonary Fibrosis Patients, N115 Non-Steroidal Nasal Spray demonstrated a statistically and clinically significant increase in Nasal Nitric Oxide, FEV-1, SaO2, FVC, FEV-1/FVC ratios (52% to 86%), and a significant reduction in coughing, nasal and lung inflammation. N115 increases Oxygen by reducing hypoxemia, and it also reduces lung inflammation, inflammatory cytokines, and coughing. These are critical benefits for treating the symptoms of Covid-19, as lung inflammation leads to pneumonia and death.

4.0 Pre-Clinical and Clinical History and Studies

4.1 Pre-Clinical Experience and Studies

As part of Cellular Science's IND submissions, five animal studies were conducted with solutions of differing concentrations of sodium pyruvate. These included a "Maximum Tolerated Nose Dose" study in rabbits (2000X the therapeutic human dose) and a 180-day nose only

inhalation study in which rats were exposed to 100 times the sodium pyruvate level expected to be administered to humans. No product related adverse reactions were observed or reported in any animal study, and the drug regimens were judged to be safe as determined by the FDA.

Rat studies in which the effect of multiple intratracheal administrations of sodium pyruvate on lung injury caused by bleomycin were conducted. Two weeks after the bleomycin insult, there was a significant (p<0.01) reduction in total cells found in the bronchoalveolar lavage containing sodium pyruvate, compared to the sodium chloride control, indicating a reduction in airway inflammation. It was concluded that sodium pyruvate was effective in reducing inflammation and lung damage in this chronic fibrotic stage of lung injury. (It should be noted that this type of injury with subsequent fibrotic infiltration is typical of the fibrosing group of interstitial diseases in humans including COVID-19.)

5.0. Qualifications of the Principal Investigator.

[name] has 15 years experience studying respiratory pathogens, developing antiviral drugs and vaccines, and studying the immune response to respiratory pathogens. [name] has designed the trial and will analyze final clinical data. [name] is a clinician and will head the clinical research and data collection.

Identification of the Research Facility

5.2. Institutional Review Board

5.3 Study Objectives

Primary Objective

- a. The primary objective is to evaluate the effects of inhaled nasal sodium pyruvate (N115) in patients with confirmed COVID-19 or flu infections by determining changes in the duration of an active infection by PCR from nasal.
 Secondary Objective
- **a.** The second objective is to evaluate the ability of the inhaled nasal sodium pyruvate therapy in subjects with COVID-19 or flu infections to improve symptoms by the use of a patient diary and by collecting periodic vital signs, especially body temperature, blood pressure and pulse/Ox.

5.4. Study Design Overview

Individuals that are symptomatic for COVID19/influenza will initially be tested by Dynamic DNA Labs or Trinity Healthcare (Screening Visit). If positive for COVID19/influenza, patient will then be solicited for participation in the trial within 24 hours. After signing Informed Consent, women of child-bearing age will provide a urine sample to test for pregnancy. They will be randomly assigned to either the placebo or drug groups in a double blinded fashion and be given a data logbook, or clinical app for their phone, in which they will record the number of coughs and other flu-like symptoms they experience each day. Patients will be contacted by phone and/or sent reminders through a clinical phone app every two days to review symptoms and protocol compliance and patients will be tested via nasal swab every other day. This will continue every other day until the subject tests negative for COVID-19/ influenza (which is

defined as a 2-Log reduction in virus titer or less than 1000 copies of viral RNA) or 14 days, whichever comes first. Personnel collecting swabs will wear N95 mask and face shield, disposable examination gloves and disposable gown while collecting nasal swabs from patients. Samples will be collected outdoors, weather permitting, or in a well ventilated room in inclement weather.

6.0. The criteria for patient selection and for exclusion of patients, and an estimate of the number of patients to be studied.

6.1. Subject Selection

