COVID-19 and flu can be understood by the region of the lung that is infected. Mild disease will be confined to the conducting airways and severe disease will involve the gas exchange portion of the lung. Both flu and COVID-19 are a major health concern and can be devastating, especially for the elderly. COVID-19 is the disease caused by SARS-CoV2 the virus. Although much is known about the mortality of the clinical disease, much less is known about its pathobiology. Although details of the cellular responses to this virus are just emerging, a probable course of events can be postulated based on past studies with SARS-CoV. Based on the cells that are infected, COVID-19 can be divided into three phases that correspond to different clinical stages of the disease. Stage #1: Asymptomatic state (Initial 1–2 days of infection); Stage #2: Upper airway and conducting airway response (Next few days), and, Stage #3 Hypoxia, ground glass infiltrates, and progression to ARDS. Flu can also result in a descending, progressive disease resulting in pneumonia and ARDS in severe cases.

Purpose and Objectives of the Studies.

A COVID-19 Non-Steroidal Nasal Spray Treatment and Preventative that can get athletes, students and the general population, that test positive for Covid-19, back playing and back to work much faster than a 14-day quarantine and as a Preventative to help reduce the rate, duration and spread of the virus, is critical to the world. In testing patients with the saliva/sputum test developed by Yale University, it was discovered that some actively infected patients may be asymptomatic, but remain infected, in some cases for three weeks or longer. Thousands of data points have been collected with the saliva/sputum tests on the duration of the infection in COVID-19 patients. This data will be used as a historical baseline to demonstrate a reduction and duration of the infection in patients that use the N115 nasal spray.

This will be an on-going trial that will study the effects of a 20mM sodium pyruvate in 0.9% sodium chloride nasal spray solution on COVID-19 viral infections of patients with proven COVID-19 infections.

1. Nasal-pharyngeal swabs that are currently FDA approved for testing COVID-19 patients, will be used to determine if an individual is actively infected.

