7.3.1. Pre-study Visit

A pre-study visit will occur and the eligibility of the subject for inclusion determined. COVID19 or influenza positive patients will sign an Informed Consent (paper or eConsent), and a list of current medications will be taken. Urine samples from child-bearing aged women will be collected and analyzed for pregnancy (or last menstrual cycle recorded). During this visit, any flu-like symptoms will be noted, temperature, Pulse/Ox and blood pressure will also be measured. During this pre-study visit, the patients are to continue with their normal therapy, if any.

7.3.2. Study Visit 1

Only COVID19 or influenza single positive subjects meeting enrollment criteria will be enrolled after review of health information collected in the pre-study visit. The correct use of the N115 sodium pyruvate nasal spray will be demonstrated to COVID-19 or influenza infected subjects, and the subjects that have been confirmed to have an infection will administer their first dose while monitored in the clinic or via telehealth. (Nasal spray can be delivered to patient at time of telehealth visit by currier). The patients will be told to spray each nostril three times, three times per day: morning, mid-day, and evening. Patients will also be instructed on filling out the Daily Data Log form or in the use of the clinical symptoms app, which will be used to record administration of the drug doses, any flu-like symptoms, and any perceived adverse events.

7.3.3 Study Visit 2 etc.

At home or on-site follow-up visits will occur every two days after Study Visit 1. During this visit, a nasal swab will be taken to determine if the patient still has an active infection. Temperature, Pulse/Ox and blood pressure will also be examined during these visits. Study monitors will review the Daily Data Log form/ Clinical app and compliance with study protocol of N115 administration will be reviewed. If needed, additional bottles of N115 nasal spray will

be delivered to the patient in the clinic or via currier.

This process of testing every two days will continue until the particular subject proves to be virus free (2 Log or greater decrease in viral RNA or less than 1000 viral RNA copies) or 14 days, whichever is first. When the patient is virus free, he/she will be excused from the study. If the subject is virus free, they will be asked to provide a second nasal swab within 24 hours to verify the negative result.

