18.5. Product Packaging

The product packaging has complied with FDA regulations. The nasal spray will be contained in a sterile plastic vial that can be squeezed to administer the correct dosage. The packaging meets 21CFR312.6 including the statement "New Drug - investigational use only." The vials necessary for each study period (i.e. ~14 days) will be placed in a plastic bag with the patient's number.

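### The primary outcome is duration of infection, but swabbing of uncleared patients stops at Day 14 and the plan has no method for them, so mean durations are capped and look short against the historical baseline

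*Combined protocol and SAP*

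**What the plan says.** - **Outcome.** The primary objective (5.3) is to assess N115 by "determining changes in the duration of an active infection by PCR from nasal" samples.
- **Observation window.** Under 5.4, "patients will be tested via nasal swab every other day", and this continues until a negative result, meaning a 2-log fall or "less than 1000 copies of viral RNA) or 14 days, whichever comes first". Section 7.3.3 repeats the limit: "or 14 days, whichever is first. When the patient is virus free, he/she will be excused from the study". Packaging (18.5) matches it: "The vials necessary for each study period (i.e. ~14 days". The schedule table runs to Day 8 and onward without naming a later swab. The only swab that could fall after Day 14 is the 24-hour confirmation in 7.3.3, which applies only to patients already negative.
- **Expected duration.** Purpose and Objectives of the Studies reports from saliva/sputum testing that "some actively infected patients may be asymptomatic, but remain infected, in some cases for three weeks or longer". It says these duration data will be the historical baseline for showing a reduction. The numbered steps that follow name Day Zero, historical baselines and placebo as comparators.
- **Motivation.** The same section wants patients "back playing and back to work much faster than a 14-day quarantine".
- **Analysis.** Section 18.2 names repeated-measures ANOVA with a baseline covariate, chi-square, Fisher and other tests, a comparison with publicly available matched data, and time dependence of titre reduction. It gives no time-to-event method, no censoring rule and no instruction for a patient still positive at Day 14.

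**The concern.** The window is at least a week shorter than some durations the protocol itself reports. For a patient still positive at Day 14 the trial knows only that the duration exceeds 14 days. Without a censoring rule, that patient and one first negative at the Day 14 swab can both be entered as 14 days.

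Two conclusions are at stake. The first is the estimated effect on duration: a mean of recorded values leaves out whatever difference between the arms lies beyond Day 14. The second is the historical comparison: trial durations that stop at 14 days would be set beside a series that does not, and the cut-off alone makes the trial patients look as if they cleared faster.

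**Working it through.** **Inputs from the documents.** Swabs fall every two days from Day 0, so clearance can be recorded at 2, 4, 6, 8, 10, 12 or 14 days. There are 15 patients per arm within each virus (6.1.1). The plan gives no distribution of durations, effect size, SD, alpha or power, so there is no planned figure to reproduce.

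**What the cap does in general.** Let S(t) be the proportion still positive at time t.

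- True mean duration = area under S(t) over all time. Capped mean = area from 0 to 14.
- The placebo-minus-N115 difference therefore loses the area between the two curves beyond Day 14. If the curves are identical nothing is lost, and no false difference between arms appears.
- Against an uncapped historical series with no drug effect, the apparent benefit is the area under S(t) beyond Day 14. It is above zero whenever anyone exceeds 14 days.

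**Size, under assumption.** Take log-normal durations with median m and SD of log time s. Write Φ for the normal distribution function and a = ln(14/m)/s.

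- Uncleared at Day 14 = 1 − Φ(a)
- True mean = m·exp(s²/2)
- Capped mean = m·exp(s²/2)·Φ(a − s) + 14·[1 − Φ(a)]

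Example with m = 10, s = 0.6: a = 0.561, and uncleared = 1 − 0.7125 = 29%. The true mean is 11.97 and the capped mean is 11.97 × 0.4844 + 14 × 0.2875 = 9.82. For N115 with m = 7, the true mean is 8.38 and the capped mean 7.69. The true difference of 3.59 days becomes 2.13, a loss of 41%.

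| Medians, placebo v N115 (s = 0.6) | Placebo uncleared at Day 14 (of 15) | True difference, days | Capped difference, days | Lost |
|---|---|---|---|---|
| 5 v 3.5 | 4% (0.6) | 1.796 | 1.644 | 8% |
| 6 v 4.2 | 8% (1.2) | 2.15 | 1.85 | 14% |
| 8 v 6 | 18% (2.6) | 2.39 | 1.70 | 29% |
| 10 v 7 | 29% (4.3) | 3.59 | 2.13 | 41% |
| 12 v 8 | 40% (6.0) | 4.79 | 2.34 | 51% |

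At s = 0.8 the losses are larger: 10 v 7 falls from 4.13 to 1.79 days (57%), and 12 v 8 from 5.51 to 1.97 days (64%), with 42% of placebo patients uncleared. These figures ignore the two-day swab grid.

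**Historical comparison with no drug effect.** At s = 0.6 and median 10, a true mean of 12.0 days is recorded as 9.8, an apparent benefit of about 2.2 days. A second assumed family, Weibull on the two-day grid with medians of 6 to 14 days, gives 0.1 to 4.1 days at shape 2 and 1.9 to 10.6 days at shape 1.

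**Would later swabs add power?** Simulated log-rank power with 15 per arm (Weibull shape 2, N115 median 0.7 times placebo), stopping at Day 14 v Day 28: 0.43 v 0.43 for placebo median 6, 0.40 v 0.42 for median 10, and 0.33 v 0.45 for median 14. The gain is small unless clearance is slow.

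**The case against.** A fixed horizon is an ordinary design choice. Both arms stop on the same day, and patients positive at Day 14 are censored, not lost. A reader might infer that the randomised comparison is biased or invalid; the documents do not support that. A comparison of clearance up to Day 14 is sound. What stands is that the plan neither limits its outcome to that window nor says how to handle those patients.

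A reader might also infer that many patients will exceed 14 days. The three-week remark concerns some COVID-19 patients, possibly asymptomatic, tested by saliva/sputum. This trial enrols symptomatic patients, uses nasal swabs, accepts a 2-log fall or fewer than 1000 copies as negative, and plans half its patients with influenza, for which no duration is given. The uncleared share could be small. This limits the size of the problem for the arm difference. It does not rescue the historical comparison, which uses the very series said to reach three weeks.

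A third tempting reading is that placebo would beat the 14-day quarantine as easily as N115, so the trial's test is empty. The quarantine appears only as motivation, and no analysis tests a mean against 14 days. The ceiling of 14 also presumes a clock starting at Day 0, which the protocol does not define.

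Finally, 18.2 does not name a mean of capped durations as its analysis, so the percentages lost describe a natural use of the data and not a stated method. That is fair, but 18.2 offers no alternative that turns these data into a duration.

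**Conclusion.** The concern holds in a limited form. Total duration of infection cannot be measured in patients uncleared at Day 14, and the plan does not say what is done with them. A mean of recorded durations understates the arm difference whenever more placebo than N115 patients remain positive after Day 14, and it favours N115 against any uncapped historical series.

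The size is not known from the documents. The 8% to 51% loss at SD 0.6 rests on assumed log-normal durations and chosen medians; short medians make it minor, and a wider spread makes it worse. The randomised comparison within 14 days is unaffected. The point should be settled before analysis because it decides what the trial may claim.

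**What to change.** In 5.3 and 18.2:

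1. Restate the primary outcome as time to clearance within 14 days of Day 0, for example mean PCR-positive days up to Day 14, and state Day 0 as the start of the clock.
2. Treat patients positive at Day 14 as censored, using a time-to-event method, and never as cleared at 14 days. In a mean up to Day 14 they contribute 14 days, which is correct for that restricted quantity but not for total duration.
3. Report the number uncleared at Day 14 by arm and by virus.
4. Truncate any historical series at the same 14-day horizon. This removes the effect of the cap, not the difference between saliva/sputum and nasal testing.
5. Make no claim against the 14-day quarantine or about durations beyond Day 14.

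The cost is a change of wording and a narrower claim.

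Optionally, patients uncleared at Day 14 could continue every-other-day swabs as observation only. To Day 28, for example, that is seven more (Days 16 to 28). Each is a home or clinic visit with vital signs, log review and staff in protective equipment, and because product is packed for about 14 days, the later durations would include time off product. This is a trade-off for the sponsor and not a requirement.

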6.1.1 Number of Patients to be Studied

Fifteen patients with confirmed COVID-19 infection will be enrolled in the trial in the drug group and fifteen with confirmed COVID-19 infection will be enrolled in the trial in the placebo group. An additional fifteen patients with confirmed influenza infection will be enrolled in the trial in the drug group and fifteen with confirmed influenza infection will be enrolled in the trial in the placebo group. Efforts will be made to include women and minorities. The study will be double blinded to subjects and study investigators.

6.2. Inclusion Criteria

- **6.2.1.** Individuals with a confirmed COVID-19/influenza viral infection, as determined by a qualified laboratory test. A nasal swab or saliva test analyzed by qPCR for COVID19 or rapid flu test from nasal swab for influenza.
- **6.2.2.** Individuals who agree to abstain from sexual intercourse, or agree to use condoms or vaginal diaphragms or other devices designed to prevent contraception, during the entire course of the study

6.3. Exclusion Criteria

- **6.3.1.** Viral infections other than COVID-19 or influenza.
- **6.3.2.** Clinically significant cardiac disease including uncontrolled congestive heart failure and unstable angina
- 6.3.3. Pregnancy
- **6.3.4.** Females of child bearing potential age not on adequate contraception or lactating
- **6.3.5.** Subjects receiving systemic corticosteroid treatment within one month of Screening Visit
- 6.3.6. Subjects Less than 18 years of age
- **6.3.7.** Hospitalization within last 6 months due to acute exacerbation of airway disease
- **6.3.8.** Subjects with a clinically significant abnormal chest x-ray within past 12 months
- **6.3.9.** Medication changes within one month of study entry
- **6.3.10.** Subjects who have participated in another investigation drug treatment study within the previous month.
- **6.3.11.** Subjects with a current history of alcohol or recreational drug abuse.
- **6.3.12.** Subjects who have taken dietary supplements containing pyruvate within 24 hours prior to the screening visit.

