18.2. Data Collection, Management, and Statistical Analysis

The data management staff at the research clinic and lab (Trinity Healthcare and Dynamic DNA Labs) will collect and manage the data. Monitoring and auditing of the data will be

conducted by a staff member of Cellular Sciences remotely.

The basic statistical analysis will be repeated measurements of Analysis of Variance using baseline measurements as a covariant per subject. Group comparisons of N115 to placebo will be analyzed by ANOVA followed by Chi Square, Fisher Exact, and other appropriate significance tests. Data will be compared to placebo controls and current publicly available matched data and observed values compared. Time dependence in viral titer reduction will also be compared. [name] will be responsible for the statistical analysis. Analysis will be performed blinded.

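### The plan does not ask for the date of first symptoms or adjust for it: lost precision between the arms, and possible bias in the external comparison

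*Combined protocol and SAP*

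**What the plan says.** **Entry.** Inclusion criterion 6.2.1 takes "Individuals with a confirmed COVID-19/influenza viral infection, as determined by a qualified laboratory test". None of the twelve exclusions in 6.3 concerns time since onset, and no minimum viral load is set. Section 5.4 requires people to be symptomatic when tested. Its only timing rule, "patient will then be solicited for participation in the trial within 24 hours", runs from the positive test and not from onset.

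**Data collected.** At the pre-study visit (7.3.1) "any flu-like symptoms will be noted"; a start date is not mentioned. The schedule (8.2) lists medical history at the pre-study visit and Day 0, and starts the symptom logbook and titre swabs at Day 0.

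**Randomisation.** Section 7.2 is one sentence and names no stratification factor.

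**Outcome and analysis.** The primary objective (5.3) is assessed by "determining changes in the duration of an active infection by PCR from nasal". Swabs are taken every two days until a 2-log fall or fewer than 1000 copies, for at most 14 days (7.3.3). Section 18.2 plans a repeated-measures ANOVA "using baseline measurements as a covariant per subject" and does not say which measurements. It also plans a comparison with publicly available matched data. The purpose statement in section 2.0 adds historical baselines on duration.

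**Course of illness.** Section 2.0 states that "COVID-19 can be divided into three phases that correspond to different clinical stages of the disease", and that some patients stay infected for three weeks or more.

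**The concern.** Follow-up starts at Day 0, so the trial observes how much longer a patient stays positive, not the whole length of the infection. Someone who enters late in the illness may have less of it left. With 15 patients per arm for each virus, randomisation can leave the arms unequal in illness day. If onset is not recorded, nobody can see such an imbalance or correct for it.

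Baseline titre is an incomplete substitute. The same Day 0 titre can belong to a patient whose virus is still rising or to one whose virus is already falling, and the first must peak before clearing. Section 18.2 does not even say that titre is the baseline covariate.

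Two things are at stake: the precision of the randomised comparison, and the fairness of the comparison with external data.

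**Working it through.** The plan gives no alpha, power, effect size or SD, so it has no figure to reproduce.

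**Inputs from the documents:** 15 per arm per virus (6.1.1), hence 30 per arm if the viruses are pooled; swabs every 2 days, and the clearance rule (7.3.3); a Day 0 titre swab (8.2).

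**Assumptions:** SD of days since onset 1 to 4; slope b = 0.5 to 1 day of remaining duration lost per extra illness day; other SD of duration 2.5 days; true effect 2 days (one swab interval); two-sided 5% test.

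**1. Chance imbalance in mean illness day.** The 95% range is ±1.96 × SD × √(2/n). For SD 2 and n = 15: 1.96 × 2 × 0.365 = 1.43.

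| Onset SD (days) | 95% range, n = 15 | Chance of ≥1 day, n = 15 | 95% range, n = 30 |
|---|---|---|---|
| 1 | ±0.72 | 0.6% | ±0.51 |
| 2 | ±1.43 | 17% | ±1.01 |
| 3 | ±2.15 | 36% | ±1.52 |
| 4 | ±2.86 | 49% | ±2.02 |

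**2. From illness day to outcome.** These figures are differences in illness day. Multiplied by b, the corresponding shift in duration at 15 per arm is about ±0.7 to 1.4 days for SD 2, ±1.1 to 2.1 for SD 3 and ±1.4 to 2.9 for SD 4.

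**3. Noise or bias between the arms.** In simulation (40,000 trials per setting, 15 per arm, SD 2 or 3, b = 0.5 or 1), overall type I error was about 5% with or without adjustment for illness day. Power for a 2-day effect changed as follows:

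| Onset SD | b | Unadjusted | Adjusted |
|---|---|---|---|
| 2 | 0.5 | 50% | 55% |
| 2 | 1 | 38% | 54% |
| 3 | 0.5 | 44% | 54% |
| 3 | 1 | 28% | 54% |

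Among null trials in which the drug arm happened to enter at least a day later, a significant result favouring the drug occurred in 9–14% unadjusted and 2–3% adjusted (nominal 2.5%). The unadjusted analysis here has no covariate at all, so the contrast does not measure the gain beyond baseline titre.

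**4. Gain beyond baseline titre.** Suppose decline is log-linear. A patient already falling from a Day 0 titre above 10^5 copies reaches the 2-log criterion after 2/rate days, whatever the illness day. Below 10^5, titre and rate fix the time to 1000 copies. Illness day therefore adds most for patients who enter before peak.

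Simulation under assumed viral curves gave a correlation of illness day with duration, given baseline titre, of about 0 to 0.46 in size. The share of residual variance removed is r², up to 0.46² = 0.21. At that upper value the sample-size equivalent is 1/(1 − 0.21) = 1.27, and the confidence interval narrows by 1 − √0.79 = 11%.

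The range is sensitive to the curves. With everyone falling, at about 0.6 log per day, the correlation was +0.04 to +0.26 (r² at most 7%). With about 40% entering while rising it was 0.45 to 0.67 in size (r² 20% to 45%).

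**5. External comparison.** If the external patients were on average d illness days away from the trial patients at their first positive sample, the expected shift in remaining duration is b × d. For d = 2 (assumed) that is 1 to 2 days. A larger sample does not shrink it.

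**The case against.** The strongest reply is that randomisation already deals with this. Imbalance in illness day is noise, the unadjusted interval includes that noise, and type I error holds. This stands. A reader might infer from the ±1.4 to 2.9 days that imbalance could overwhelm the duration comparison. The documents do not support that: the figure is in illness days, the slope and onset SD are assumed, and at an SD of 1 day the effect is minor.

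A second reply is that a baseline covariate is already planned and a Day 0 titre is taken, so only the gain beyond titre counts. This also stands. Crediting onset with all the variance it would explain in a model with no covariates (9–36% for correlations of 0.3–0.6) would overstate the benefit. The extra gain rests mainly on patients entering before peak. Section 2.0 describes clinical stages, for COVID-19 only and as a postulated course, and gives no titre curves.

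Two further readings go too far. Entry is not open at every stage, because 5.4 screens out people without symptoms. Nor can one say that the onset date will go uncollected: medical history or the case report form, which is not among the documents, may capture it. The supportable statement is that the plan does not specify it.

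Finally, 18.2 sets out no explicit model for duration, and defining one comes before choosing covariates. That is fair, but the onset date has to be asked for at entry whichever model follows. None of these replies protects the external comparison.

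**Conclusion.** The gap is real and modest. The plan specifies neither the date of first symptoms as a data item nor time since onset as a covariate. For the randomised comparison the consequence is lost precision and possible chance imbalance, without systematic bias or an inflated overall error rate. Given an onset SD of 2 to 4 days, the imbalance range is ±1.4 to 2.9 illness days at 15 per arm and ±1.0 to 2.0 at 30.

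The gain from adjustment beyond baseline titre cannot be fixed from the documents. It may be near zero or about 20% of residual variance, and the share entering before peak titre decides which; the upper figure is not a ceiling.

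The firmer reason to act is the comparison with historical baselines and public matched data. Without onset dates, illness stage can be neither matched nor examined there, and a difference in stage would appear as a difference in duration.

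**What to change.** - At the pre-study visit, where symptoms are already noted, record the date of first symptom.
- Tabulate days since onset by arm within each virus.
- In 18.2, name days since onset and baseline log titre as prespecified covariates in the analysis of duration of infection.
- Use days since onset when matching or interpreting the historical and public data. If an external source does not report it, state that as a limitation.

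No limit on time since onset is needed for entry, so recruitment is unaffected. The cost is one form field, some recall error in the date, and one degree of freedom.
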